Individual vials containing 10 mL of enriched heparin (250 μ g/mL, that will be adjusted after the filtration process based on the result of biochemical analysis) or placebo (adding to the same total volume of 0.9% saline solution) will be prepared by the pharmacist, stored in a freezer at -30° Celsius, and delivered to the research team in a blind character. After receiving the preparation (enriched heparin or placebo), it must be inserted into the nebulizer cup and administered in a source of oxygen or compressed air (5L/min or according to the patient's need) in isolated rooms, a process that spend 30 minutes. Nebulization therapy will be performed after isolation of the patient and with support from the hospital infection control committee, so that there will be no greater risk of spreading the virus.

Eligibility criteria

Sign and agree to the free and informed consent form;

Both sexes, of any ethnic origin, aged between 18 and 90 years;

COVID-19 infected, diagnosed by reverse-transcriptase polymerase chain reaction (RT-PCR) or with a strong suspicion of COVID-19 through compatible clinical and radiological findings;

Time of disease evolution less than 10 days;

Radiological diagnosis of grade IIA pneumonia, with gas exchange ratio >200 in blood gas analysis (paO₂ / pFiO₂), characterizing mild hypoxemia;

Indication of hospital treatment regime, provided that the period of hospitalization before inclusion is not more than 24 hours;

Demand for supplemental oxygen therapy (O₂) less than 5 L/min.

Exclusion criteria

Disagree with the terms of the study;

Moderate or severe respiratory failure requiring ICU admission requiring invasive mechanical ventilation or positive pressure non-invasive ventilation (NIV);

Pregnancy or puerperium;

Hematological diseases;

Coagulation disorders;

Previous use of anticoagulants in therapeutic dosages for more than 72 hours;

Previous heparin-induced allergy or thrombocytopenia or current thrombocytopenia with a count of less than 50,000 platelets/mm³.

Discontinuation criteria

Participants can withdraw from the study, if they wish, at any time and regardless of the reason, without consent of the research team. Any type of severe adverse events, according to the rules of the Common Terminology Criteria for Adverse Events (CTC-AE 5.0)²⁵ will be considered criteria for discontinuation.

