The reasons for discontinuing treatment will be properly documented by the research team and, in case the study is closed, the researchers will ensure the continuity of the medical and hospital assistance to the participant.

If COVID-19 is not confirmed by RT-PCR within 72 hours of the inclusion, the patient will be withdrawn from the study.

Randomization and study arms

Participants will be divided in two groups and randomized 1:1. In this way, they will receive a sequential inclusion number from an electronically drawn number table and will receive the treatment according to the allocation in one of the groups:

Group 1 - Control: Nebulization with 10mL of 0.9% saline solution, administered every 4 hours for 7 days, except the nebulization that would be administered between 12pm and 6 am (5 inhalations per day).

Group 2 - Experimental: Nebulization with enriched heparin (250 μ g/mL diluted in 10mL of 0.9% saline solution), administered every 4 hours, for 7 days, except the nebulization that would be administered between 12 pm and 6 am (5 inhalations per day).

The randomization list will be prepared by an independent statistician, using Stat Trek, a program to construct random number tables, available at <http://stattrek.com/Tables/Random.aspx>. Fifty positions will be drawn in a random and consecutive manner. The envelope containing the randomization will be kept in possession of an independent professional (pharmacist), so that the members of the study team will not know the order of allocation.

Blinding

The clinical trial will be triple-blind. Participants, researchers, the data and statistical analysis team will not have access to the allocation numbers. A pharmacist will produce the heparin and the placebo and will assign a researcher of the team to distribute the product to each participant, according to the randomization list. In addition, presentation of the preparation to the control and experimental group will be identical, since enriched heparin is colorless and odorless to the human eye and nose, as well as the saline solution. The blinding code will not be broken until all research participants have completed the study and the database is closed, that is, it will not undergo further changes. In an emergency, and if necessary, members of the data and security monitoring committee can request a blinding break, only for the participant at risk.

Sample size, recruiting and statistical analysis

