The total recruitment size will be 50 participants, aiming at 40 patients followed during the study period. The sample was estimated considering the number of patients diagnosed as COVID-19 at the São Paulo State University (UNESP) Clinical Hospital that met the study's eligibility criteria.

The sample calculation of 40 patients took into account two independent study arms, with an estimated proportion in the viral load reduction rate of 30% for group 1, that will receive placebo, and 75% for group 2 that will be treated with enriched nebulized heparin as proposed in this study, considering 80% test power and a 5% significance level for a bilateral test.

Categorical variables will be evaluated with Fisher's exact test, continuous variables will be compared with non-parametric methods such as Mann-Whitney test or U test, paired comparisons will be evaluated with the Wilcoxon test, multivariate analyzes will be evaluated with regression Cox analysis and long-term clinical analyzes will be compiled on Kaplan-Meir curves.

Interventions and inpatient schedule

Intervention	Day 0	Day 1	Day 2	Day 3	Day 4	Day 5	Day 6	Day 7	Day 8
Informed consent form	X								
Medical visit, patient story and physical examination	X	X	X	X	X	X	X	X	X
Vital signs assessment	X	X	X	X	X	X	X	X	X
Medications in use	X	X	X	X	X	X	X	X	X
Inclusion and exclusion criteria	X								
COVID-19 viral load in RT-qPCR	X		X			X		X	X
Complete blood count, D-dimer, aPTT, urea, creatinine, glucose, reactive protein C, blood gas and amylase	X		X			X		X	X
Computed thoracic tomography	X								X
HMWH or placebo administration		X	X	X	X	X	X	X	X
Adverse events	X	X	X	X	X	X	X	X	X
Discontinuation criteria	X	X	X	X	X	X	X	X	

Table 1. Schedule for assessments and intervention. The participants will be followed up and evaluated on days 0, 1, 2, 3, 4, 5, 6, 7 and 8 days after randomization.

The closure assessment will be carried out on day 8. Extra data can be collected if the patient's clinical condition changes. Randomization will be performed in up to 24 hours after admission. After the end of the study, the participant will be referred and accompanied at the COVID-19 outpatient clinic São Paulo State University (UNESP) Clinical Hospital.

Adverse events

Adverse effects related to the nebulized use of heparins will be tracked and analyzed according to the Common Terminology Criteria for Adverse Events (CTC-AE 5.0),²⁵ and will be graded from 1 to 5, accordingly to the severity of the event.

Grade	Description

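### The 72-hour PCR rule can end scheduled safety assessment of patients already dosed, and nothing in the supplied text keeps them in the primary safety comparison

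*Combined protocol and SAP*

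**What the plan says.** Under Eligibility criteria, a patient may enter with a positive RT-PCR or "with a strong suspicion of COVID-19 through compatible clinical and radiological findings". Inclusion numbers come from the randomisation table (Randomization and study arms), and randomisation takes place within 24 hours of admission (text after Table 1). Nothing supplied makes dosing wait for the PCR result.

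Study treatment is "administered every 4 hours for 7 days", with one overnight dose omitted, which the plan gives as five inhalations a day. In Table 1 the row "HMWH or placebo administration" is marked from Day 1.

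Under Discontinuation criteria: "If COVID-19 is not confirmed by RT-PCR within 72 hours of the inclusion, the patient will be withdrawn from the study". The sentence before it concerns treatment: "The reasons for discontinuing treatment will be properly documented by the research team".

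The Table 1 caption reads: "The participants will be followed up and evaluated on days 0, 1, 2, 3, 4, 5, 6, 7 and 8 days after randomization". The row "Complete blood count, D-dimer, aPTT, urea, creatinine, glucose, reactive protein C, blood gas and amylase" is marked on Days 0, 2, 5, 7 and 8, and the adverse event row on every day from 0 to 8. On numbers: "The total recruitment size will be 50 participants, aiming at 40 patients followed during the study period".

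The statistical paragraph names tests but no analysis population. No supplied text says how patients removed by the 72-hour rule are followed or analysed.

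**The concern.** The study design section gives safety as the main intention, and the primary safety items are bleeding of any kind, prolonged aPTT and heparin-induced thrombocytopenia. The last two depend on scheduled blood tests. The Adverse events section defines thrombocytopenia through a fall in platelet count, so serial counts are needed to see it.

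Exposure to the nebulised product does not depend on the PCR result. A patient who has inhaled it for two or three days carries safety information whether or not infection is later confirmed. A rule that takes such a patient out of the study cuts that information short. Unlike voluntary withdrawal, the protocol imposes this loss on people who may be willing to go on being assessed.

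**Working it through.** **Inputs from the documents.** Five inhalations a day (Randomization and study arms); treatment for 7 days (same section) but marked on Days 1 to 8 in Table 1; blood draws on Days 0, 2, 5, 7 and 8; adverse event checks on Days 0 to 8; tomography on Days 0 and 8; 50 recruited and 40 followed.

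**The plan's own figures.** A 4-hourly schedule gives 24/4 = 6 doses a day; omitting one leaves 5, as stated. Over 7 days that is 7 × 5 = 35. The Table 1 row gives 8 × 5 = 40. These two passages conflict and must be reconciled. The allowance for loss is (50 − 40)/50 = 20%; the plan does not say what it is made up of.

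**One dosed patient withdrawn at exactly 72 hours.** Assume inclusion falls on Day 0 and dosing follows Table 1.

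| | Included early on Day 0 | Included late on Day 0 |
|---|---|---|
| 72 hours ends | as Day 3 starts | late on Day 3 |
| Inhalations received | Days 1–2: 2 × 5 = 10 | Days 1–3: 3 × 5 = 15 |
| Share of 35 | 10/35 = 28.6% | 15/35 = 42.9% |
| Share of 40 | 10/40 = 25.0% | 15/40 = 37.5% |
| Post-dose blood draws lost | Days 5, 7, 8: 3 of 4 | Days 5, 7, 8: 3 of 4 |
| Adverse event checks lost, of Days 1–8 | Days 3–8: 6 of 8 | Days 4–8: 5 of 8 |
| Post-dose tomography lost | Day 8: 1 of 1 | Day 8: 1 of 1 |

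Only the Day 2 draw remains, so there is one scheduled post-dose platelet count and one post-dose aPTT. Earlier withdrawal loses more assessments but after fewer doses. A patient withdrawn before any dose is outside this point.

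**Trial level, illustration only.** The documents give no number of affected patients. If *k* are dosed and withdrawn at 72 hours, the loss is 3*k* of 50 × 4 = 200 post-dose draws and 5*k* to 6*k* of 50 × 8 = 400 checks.

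- Assumed *k* = 2: 6/200 = 3% of draws; 10/400 to 12/400 = 2.5% to 3% of checks.
- Assumed *k* = 10, which would use the whole 50-to-40 allowance: 30/200 = 15% of draws; 50/400 to 60/400 = 12.5% to 15% of checks.

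The true number could lie below this range and could be zero.

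**The case against.** **The target population.** The primary safety objective is worded around people with SARS-CoV-2 infection. A patient who is never confirmed arguably falls outside it, which makes the rule consistent with the objective. This stands in part: keeping such patients widens the stated population, and the plan would have to say so. It does not remove the reason to follow patients whom the protocol itself exposed.

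**Loose terms.** Under one heading the plan moves between leaving the study and stopping treatment, and the Adverse events section is no tighter. The rule may have been meant as a treatment rule. This stands, and it is why the conclusion is that follow-up can end, not that it must.

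**Other text covers these patients.** The Table 1 caption is general. Adverse effects of nebulised heparin are to be tracked and analysed, severe effects noted by the researchers go to the monitoring committee, and extra data may be collected if the clinical condition changes. None of this mentions patients removed by the 72-hour rule, and none restores the scheduled platelet and aPTT draws.

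**The gap is wider.** Voluntary withdrawals and discontinuations for severe events also have no stated analysis population. That is true, but here a specific rule causes the loss, and changing its wording removes it.

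**Stronger readings.** A reader might infer that data already collected are thrown away, or that the safety estimate loses a definite amount of precision. The documents do not say that data are discarded, and they give neither the number affected nor its split by arm. A reader might also infer bias between arms, because the rule does not name the confirming sample and the Day 2 swab is taken on treatment. That would require the Day 2 swab to decide retention, which the documents do not say.

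**Conclusion.** The point holds in a limited form. The plan allows unconfirmed entry, starts dosing before the 72-hour limit, and then withdraws unconfirmed patients from the study. Read as written, that can end scheduled safety assessment of exposed patients, and no supplied text keeps them in the primary safety comparison.

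For each such patient the loss is large: three quarters of the post-dose blood draws and most of the adverse event checks, after roughly a quarter to two fifths of the planned doses. For the trial as a whole the size is unknown and may be small.

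The conclusion rests on the literal reading of the rule, on inclusion falling on Day 0, on dosing as in Table 1, and on withdrawal at the full 72 hours. The main cost is incomplete safety follow-up. The change is worth making because it is cheap and serves the trial's main purpose. Confidence is medium, given the loose wording.

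**What to change.** Replace the wording on withdrawal from the study so that:

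- patients unconfirmed at 72 hours leave only the main efficacy set;
- every patient with at least one nebulisation stays in the safety set by allocated arm and, subject to consent, completes the adverse event checks and the blood count and aPTT draws already in Table 1, to Day 8 or discharge (this change does not require the Day 8 tomography or the blood gas);
- unconfirmed patients are reported by arm, with an all-randomised sensitivity analysis of efficacy.

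State that the safety set then includes exposed patients without confirmed infection, which is wider than the wording of the primary safety objective, and report the confirmed subset alongside it.

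As a clarification only, name the sample that counts for confirmation. Reconcile the 7-day text with the Day 1 to Day 8 administration row. Whether study treatment continues in unconfirmed patients is for the sponsor to decide.

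**Cost.** New wording, a little more follow-up work, and a few further blood draws in patients without confirmed COVID-19. For some of them safety data will still stop at discharge.

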A study carried out by Bendstrup, et al (2002),¹⁷ evaluated the effects of the inhibition of systemic coagulation through nebulized unfractionated heparin at doses up to 64 mg and identified that there is a dose-dependent effect for factor Xa inactivation, inducing minimal changes in aPTT, and it is safe for clinical or research purposes, without increasing the risk of bleeding.¹⁸

Phelps, et al (2020),¹⁹ carried out a systematic review on the use of UFH inhalation for the treatment of inhalation injury caused by heat in burn patients and concluded that nebulized heparin did not demonstrate an increase in the risk of bleeding rates and decreased the duration of mechanical ventilation.

For COVID-19, the heparin anti-viral effect is expected to be related to the fact that heparin blocks viral interaction with host receptors thereby inhibiting virus interaction with the cell and, consequently, viral invasion.^{20, 21} To this moment, some studies indicate that treatment with systemic heparin reduced hospital mortality in patients with COVID-19²² and a previous study that strongly supported the clinical investigation of heparin as a potential treatment for patients with COVID-19,^{23, 24} justifies further investigation to prove these clinical effects.

Objectives

Primary objectives assessment

Safety: related to the use of nebulized enriched heparin by patients with SARS-CoV-2 through the assessment of hemorrhagic events of any nature, alteration of the coagulation testing, like prolonged activated partial thromboplastin time (aPTT), indicated by an increase in aPTT>1.5, and heparin-induced thrombocytopenia; Efficacy: related to the proposed treatment, through analysis of the SARS-CoV-2 viral load of the participants treated by the sequential assessment of reverse transcription-polymerase chain reaction (RT-PCR) in the nasal swab.

Secondary objectives assessment

Safety measured by respiratory, clinical, laboratorial and tomographic findings as follows, in number of patients, and hospitalization days:

Supplemental oxygen therapy needed;

Mechanical pulmonary ventilation needed;

Renal failure development;

Development of major cardiovascular events such as pulmonary embolism and acute myocardial infarction;

Demand for intensive care unit (ICU) treatment;

Secondary pulmonary bacterial infections (bacterial pneumonia);

Deep vein thrombosis (DVT) through Doppler ultrasonography assessment;

Pancreatitis characterized by increase in amylase >200 U/L;

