Aphasia	Yes 	No 	
Aphasia start date (blank if not present)			
Aphasia end date (blank if still present)			
Hyporexia	Yes 	No 	
Hyporexia start date (blank if not present)			
Hyporexia end date (blank if still present)			
Heart rate (BPM)			

Brachial systolic pressure (mmHg)					
Brachial diastolic pressure (mmHg)					
Peripheral oxygen saturation (%)					
Axillary temperature (Celsius)					
Paleness	Normal 	1+/4+ 	2+/4+ 	3+/4+ 	4+/4+ 
Cyanosis	Normal 	1+/4+ 	2+/4+ 	3+/4+ 	4+/4+ 
Oral cavity	Normal 	Altered 			
Description					
Pulmonary auscultation	Normal 	Altered 			
Description					
Cardiac auscultation	Normal 	Altered 			
Description					
Abdominal examination	Normal 	Altered 			
Description					
Limbs (pulses, edema, skin conditions)	Normal 	Altered 			
Description					

Figure 2. Clinical assessment and physical examination form based on SARS-CoV-2 most prevalent symptoms.

Laboratory results and tomographic findings form			
Form Number:	Date:		
RT-qPCR	Positive 	Negative 	
RT-qPCR quantitative viral load			
Blood count	Normal 	Altered 	
Hemoglobin (g / dL)			
Hematocrit (%)			
Mean corpuscular volume (fL)			
Red cell distribution width (%)			
Platelets count (10³ / µL)			
White cell count (10³ / µL)			
Neutrophils (%)			
Lymphocytes (%)			
Bands (%)			
Arterial gas	Normal 	Altered 	
pH			
pCO₂ (mmHg)			
PaO₂ / FiO₂			
HCO₃ (mEq / L)			
SO₂ (%)			
Base Excess			
D-Dimer (µg / mL)			
aPTT	Normal 	Altered 	
Prothrombin time (PT)			
International normalized ratio (INR)			
Activated partial thromboplastin time (aPTT)			
Normalized aPTT Ratio			
Renal function	Normal 	Altered 	
Urea (mg / dL)			
Creatinine (mg / dL)			

Fasted glucose (mg / dL)	
C reactive protein (CRP) (mg / L)	
Amylase (U / L)	
Thoracic tomography description	

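### Viral load is measured quantitatively but sized as a yes/no reduction, and no test is tied to the primary comparison; analysed as sized, with Fisher's test, power at 20 per arm is 73%, not 80%

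*Combined protocol and SAP*

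**What the plan says.** **Objective.** Under "Primary objectives assessment", efficacy is to be judged "through analysis of the SARS-CoV-2 viral load of the participants treated by the sequential assessment of reverse transcription-polymerase chain reaction (RT-PCR") in the nasal swab. No responder threshold, day or between-arm test is given there.

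**Measurement.** Table 1 schedules RT-qPCR viral load on Days 0, 2, 5, 7 and 8. The laboratory form (Figure 3) has a positive/negative box and a separate field, "RT-qPCR quantitative viral load".

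**Sizing.** The section on sample size and statistical analysis sets the effect "with an estimated proportion in the viral load reduction rate of 30% for group 1, that will receive placebo, and 75% for group 2", "considering 80% test power and a 5% significance level for a bilateral test". It also says: "The total recruitment size will be 50 participants, aiming at 40 patients followed during the study period". With 1:1 allocation, that is 20 followed per arm.

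**Tests.** The same section says: "Categorical variables will be evaluated with Fisher's exact test, continuous variables will be compared with non-parametric methods such as Mann-Whitney test or U test". Nothing assigns the primary viral-load comparison to either test.

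**The concern.** The primary efficacy variable is a number measured five times, but the only efficacy hypothesis reduces it to whether a patient had a reduction. On that scale, a patient who just passes the cut and a patient who clears the virus count the same. The plan gives no clinical or regulatory reason for a cut.

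Two things are at stake. First, if the analysis follows the sizing, the test that the plan names for categorical data may not deliver the stated power. Second, a full-scale test is already in the plan and might use the same swabs better, but nothing commits the trial to it. As written, either scale could be chosen at the analysis stage.

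Defining the cut more carefully would not settle this. A clearly defined responder endpoint with the same 30% and 75%, tested by Fisher at 20 per arm, has the same power.

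**Working it through.** **Inputs from the protocol.** Proportions 0.30 and 0.75; two-sided 5% level; 80% power; 1:1 allocation; 40 followed (20 per arm) of 50 recruited. **Not in the protocol:** any SD, distribution or correlation for viral load.

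**Step 1. Reproduce the plan's figure.** Pooled two-proportion formula, no continuity correction, with mean proportion (0.30 + 0.75)/2 = 0.525:

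n per arm = [1.960 × √(2 × 0.525 × 0.475) + 0.842 × √(0.30 × 0.70 + 0.75 × 0.25)]² / 0.45²
= [1.384 + 0.531]² / 0.2025 = 18.1, rounded up to 19, or 38 in total.

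This is within 2 of the stated 40, so the sizing behaves as a comparison of two proportions. The same formula gives 84.1% power at 20 per arm. With a continuity correction it needs 23 per arm (46).

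**Step 2. Exact power on the cut.** Sum the binomial probabilities of all pairs of responder counts for which the test gives p ≤ 0.05.

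| Per arm | Fisher's exact | Chi-square, uncorrected |
|---|---|---|
| 20 | 73.1% | 82.3% |
| 22 | 79.5% | 87.4% |
| 23 | 82.8% | 89.7% |
| 25 | 88.1% | 93.1% |

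At the planned 20 per arm, Fisher is about 7 points below the stated 80%. The gap between the two tests, 82.3 − 73.1 = 9.2 points, comes from Fisher's conservatism and not from the cut. No assumption about the shape of viral load enters this step.

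**Step 3. Full scale, if heparin shifts the whole distribution.** Assume that log viral-load change has the same shape in both arms, and that 30% and 75% are the shares past a common cut. For a normal shape the shift is z(0.75) − z(0.30) = 0.674 + 0.524 = 1.20 SD. The other shapes use their own quantiles in the same way. Simulated Mann-Whitney power at 20 per arm (20,000 runs, two-sided 5%):

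| Assumed shape | Mann-Whitney | Gain over Fisher (73.1%) | Gain over chi-square (82.3%) |
|---|---|---|---|
| Normal | 94.8% | 21.8 | 12.5 |
| Logistic | 92.1% | 19.0 | 9.8 |
| t, 5 df | 90.8% | 17.8 | 8.5 |
| t, 3 df | 87.6% | 14.5 | 5.3 |
| Laplace | 83.8% | 10.7 | 1.5 |

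(Gains are in percentage points, from unrounded powers.) If the normal shift holds but every value past the cut is tied at a detection floor, Mann-Whitney power is 90.0%.

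**Step 4. Full scale, if heparin changes only the share of responders.** Assume that 30% and 75% respond and that values within responders, and within non-responders, are alike in the two arms. With clearly separated classes, Mann-Whitney power is about 71%, slightly below Fisher. With responders tied at a floor it is about 78%: 5 points above Fisher and below chi-square. If the classes overlap, power is lower still.

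**Step 5. What these steps separate.** Step 2 is the cost of using Fisher on the endpoint as sized. Steps 3 and 4 show that the further cost of the cut itself depends on how heparin acts, and the documents do not say.

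**The case against.** **The plan never says that the primary test is binary.** A reader might infer from the sizing sentence that the trial has committed to a dichotomised primary analysis. The documents do not support that. The objective names viral load itself, the form records a number, and Mann-Whitney is listed for continuous variables. Sizing on a proportion does not fix the analysis. This stands: the loss is conditional on analysing the endpoint as it was sized.

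**The gain has no single size.** A reader might also take the normal-shift result and say that the cut costs 15 to 22 points, or that the full-scale test has 88% to 95% power. Neither holds as a general figure. About 9 points of the gap belong to Fisher, a Laplace shape already gives 84%, and a responder mixture can remove the gain altogether. This also stands.

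**The proportion reading is not explicit.** The phrase about a reduction rate could mean an average percentage reduction. A difference of 45 points with an assumed SD of 50 points needs 2 × (1.960 + 0.842)² × 50²/45² = 19.4, or 20 per arm. But no SD is given, and a suitable SD would match any sample size, while the text speaks of a proportion. Two proportions is the likelier reading. If a mean was intended, the 73% does not apply, but the endpoint still has to be stated.

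**Safety comes first, and more than 40 may be evaluable.** The study design section presents this as a small phase I/II trial whose chief purpose is safety, which limits the weight of any efficacy power figure. With all 50 evaluable, Fisher would have 88% power; the plan itself aims at 40. Efficacy remains a stated primary objective with its own power claim, so that claim should match the test.

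**Conclusion.** The concern holds in a conditional form. The efficacy hypothesis and sample size treat a quantitative, repeatedly measured variable as yes/no, and the plan leaves the primary comparison tied to neither named test.

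The firm number is 73%. It is the exact power of Fisher's test for 30% versus 75% at 20 per arm, and it rests only on the plan's own inputs and on the proportion reading. Chi-square on the same cut has 82%.

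The possible benefit of the full scale is less certain. It is about 11 to 22 points over Fisher, and about 2 to 13 over chi-square, if heparin shifts the whole distribution with a Laplace to normal shape. It is from slightly negative to about 5 points over Fisher in the responder-share scenarios with clearly separated classes or a floor, and worse if the classes overlap.

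This should be changed before analysis. The quantitative comparison suits the stated objective, uses data already collected and follows a method already named. The case for it does not depend on promising a particular power.

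**What to change.** In the statistical section:

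1. State that the primary between-arm efficacy comparison is the change in log10 viral load (or Ct) from Day 0 to a named day, tested by Mann-Whitney or by a rank or linear model adjusted for the Day 0 value.
2. Add a tie rule: an undetectable result takes the best (lowest-load) rank, with the direction reversed if Ct is used.
3. Keep the proportion with a reduction, once defined, as a secondary summary by arm with a confidence interval for the difference.
4. Restate the power: about 73% for Fisher on 30% versus 75% at 20 per arm. Give any full-scale power only with its distributional assumption and a range that includes a responder-share scenario.

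The cost is a few sentences and a restated power figure, with no added patients, swabs or procedures. The small downside is that the headline result becomes a difference in log10 load rather than a simple percentage, and that undetectable results need the tie rule.

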Demand for corticosteroid therapy such as hydrocortisone, dexamethasone and other corticosteroids due to inflammatory pulmonary disease;

Death;

Increase in white blood cell count (>10.000 cells/mm³);

Increase in C reactive protein test (CRP) (>3.00mg/L);

Deterioration of arterial blood gas paO₂/pFiO₂ ratio (<200);

Altered sodium (< 135mEq/L or > 145mEq/L);

Altered potassium (< 3,5mEq/L or > 5,5mEq/L);

Worsening of pulmonary area compromised (%) by inflammation or infection through tomographic assessment.

Method

EnHanCed study design

The present protocol refers to a phase I / II, prospective, randomized, parallel, triple blind clinical trial. This design is justified by the lack of a drug-specific cost-efficient treatment for SARS-CoV-2 patients. The use of a therapeutic drug justifies the need for a placebo control group. A minimum number of participants will be allocated to this study, as the main intention will be to evaluate the safety of the treatment. Triple blind clinical studies have the lowest levels of bias and, therefore, the highest level of evidence for a clinical study. It is understood that there is no need for a purely phase I study based on the literature data previously presented.

The study will be carried out at the São Paulo State University (UNESP) Clinical Hospital of the Botucatu Medical School, Botucatu, São Paulo, Brazil.

Dosage and administration

Considering the pulmonary water loss of 8 to 10mL during the gas exchange in 30 minutes (of inhalation) and compensating the dilution of the solution in the pulmonary fluids, we opted for the dose of 2.5 mg heparin in 10mL of 0.9% saline solution, aiming the effective mean tested doses (62.5 μ g/mL to 250 μ g/mL), nebulized 4/4 hours, except the nebulization that would be administered between 12 pm and 6 am. The treatment will be administered for 7 days because it will be assumed that the reduction in viral load promoted by enriched heparin will have a significant impact during the first 14 days of the infectious process. Considering that the patient has already had the disease for at least seven days when admitted and that the viral load tends to reduce spontaneously after the referred period, it is known that complications persist due to other factors such as inflammatory response.

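### The 30% placebo rate used to size the trial has no source and no threshold, and it sits uneasily with the plan's own account of spontaneous viral decline, so the stated 80% power is not secure

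*Combined protocol and SAP*

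**What the plan says.** In the combined protocol and SAP, the section on sample size, recruiting and statistical analysis gives these inputs:

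- Rates: an "estimated proportion in the viral load reduction rate of 30% for group 1, that will receive placebo, and 75% for group 2".
- Error rates: "considering 80% test power and a 5% significance level for a bilateral test".
- Numbers: "The total recruitment size will be 50 participants, aiming at 40 patients followed during the study period". Under Randomization and study arms, "Participants will be divided in two groups and randomized 1:1", which gives 20 followed per arm.
- Test: "Categorical variables will be evaluated with Fisher's exact test". Continuous variables get a rank test. The section does not say which of the two applies to viral load.
- Other basis for the number: "The sample was estimated considering the number of patients diagnosed as COVID-19" at the hospital who met the eligibility criteria. This speaks to feasibility and does not support the 30%.

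The section on dosage and administration justifies the length of treatment in these terms: "Considering that the patient has already had the disease for at least seven days when admitted and that the viral load tends to reduce spontaneously". The full clause is "viral load tends to reduce spontaneously after the referred period". It attaches no rate or size to that decline.

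Viral load by sequential nasal swab is the primary efficacy objective. Table 1 schedules it on Days 0, 2, 5, 7 and 8. Nowhere is a reduction defined by size or by day.

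**The concern.** The control arm inhales saline and is swabbed until Day 8. If most of these patients are a week or more into the illness and their viral load is already declining, many would be expected to show some fall without heparin. The sizing assumes that fewer than one in three will. Both statements can be true only if reduction means something more than the natural decline, and the plan sets no such bar.

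Power depends heavily on this one number. If the placebo rate is higher and the heparin rate does not rise with it, the contrast shrinks quickly, and a null result on the primary efficacy objective could be given more weight than the design can bear. If any fall counts, the endpoint may also reach a ceiling at which no advantage for heparin could be detected.

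**Working it through.** **Inputs.** From the plan: 30% v 75%, 80% power, two-sided 5%, 40 followed, 1:1 allocation. Assumed: exactly 20 per arm, the sized proportion analysed as a categorical variable by Fisher's exact test, and every placebo rate above 30%.

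**Step 1. Reproduce the plan's figure.** Pooled normal formula without continuity correction, with mean rate (0.30 + 0.75)/2 = 0.525:

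n per arm = [1.960 × √(2 × 0.525 × 0.475) + 0.842 × √(0.30 × 0.70 + 0.75 × 0.25)]² / 0.45²
= [1.960 × 0.706 + 0.842 × 0.630]² / 0.2025 = 18.1, rounded up to 19.

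That is 38 in total, within two patients of the stated 40. At 20 per arm the same approximation gives 84% power. The arithmetic of the plan is therefore in order.

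**Step 2. Power under the named test.** List all 21 × 21 outcomes for 20 v 20, mark those with two-sided Fisher p ≤ 0.05, and sum their binomial probabilities. At 30% v 75% the result is 73%. Fisher's test first reaches 80% at 23 per arm (83%).

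**Step 3. Vary the placebo rate.** The plan's odds ratio is (0.75/0.25)/(0.30/0.70) = 7. Holding it fixed, the heparin rate is 7o/(1 + 7o), where o is the placebo odds. At a placebo rate of 50%, for example, o = 1 and the heparin rate is 7/8 = 87.5%.

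| Placebo rate | Heparin 75%: normal approx. | Heparin 75%: Fisher | Heparin rate at odds ratio 7 | Odds ratio 7: Fisher |
|---|---|---|---|---|
| 30% | 84% | 73% | 75.0% | 73% |
| 40% | 62% | 49% | 82.4% | 72% |
| 50% | 37% | 27% | 87.5% | 66% |
| 60% | 17% | 11% | 91.3% | 55% |
| 70% | 5% | 3% | 94.2% | 41% |

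**Step 4. When power is kept.** The 45-point gap need not be preserved. Fisher power stays at 73% for 50% v 89.7% (a gap of about 40 points) and for 60% v 95.3% (about 35 points). Keeping all 45 points at a placebo rate of 50% (50% v 95%) raises power to 89%.

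**Step 5. The ceiling.** Give heparin its best possible result, 20 of 20. With k placebo patients showing no fall, the two-sided Fisher p-value is 2 × C(20,k)/C(40,k).

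- k = 5 (15/20 v 20/20): 2 × 15,504/658,008 = 0.047.
- k = 4 (16/20 v 20/20): 2 × 4,845/91,390 = 0.106.

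Once 16 or more of 20 placebo patients count as reduced, no result in favour of heparin reaches p ≤ 0.05.

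**The case against.** The strongest reply is that the plan does not contradict itself, and that reply is right. A reader might infer that the dosing section disproves the 30%, but it does not:

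- Its statement is qualitative and gives no rate to set against 30%.
- The period it refers to may be the seven days before admission, or the 14 days named in the sentence before. On the second reading, much of the decline would come at or after the Day 8 swab.
- The eligibility criteria require less than 10 days of illness and set no lower limit, so a week of illness describes the expected patient and is not an entry condition.
- Under a strict criterion, such as a large log fall or a negative swab by a fixed day, 30% on saline could be reasonable.

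Two further points also stand. Holding heparin at 75% while placebo rises is the least favourable of the scenarios shown. Spontaneous decline acts in both arms, and with the odds ratio held at 7 a placebo rate of 40% costs almost nothing (72% against 73%). Also, Fisher's test for this endpoint is inferred: the laboratory form records a quantitative viral load, and a rank comparison of that measure would not have the ceiling in step 5.

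The plan also says that it enrols a minimum number because safety is the main intention. That lessens the consequence of low power, but viral load remains a primary objective and the 80% claim is made for it.

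What survives is that the 30% has no stated basis, the event it describes is undefined, and nothing in the plan reconciles it with the expected decline.

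**Conclusion.** The concern holds as an unsupported and unreconciled assumption. It does not hold as a contradiction or as an arithmetic error. The stated 40 follows from the plan's inputs by the pooled formula, but Fisher's test at 20 per arm delivers 73% at the plan's own rates, not 80%.

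Beyond that, the loss depends on figures the plan does not give. For placebo rates of 40% to 60%, power runs from 49% down to 11% if heparin stays at 75%, and from 72% down to 55% if the odds ratio stays at 7. It is not lost at all if the heparin rate rises enough, for example to about 90% against a placebo rate of 50%. A reader might infer that power survives only if the full 45-point gap is kept. The enumeration shows that a smaller gap is enough at higher rates.

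These results assume 20 evaluable patients per arm and a responder analysis by Fisher's test. The ceiling matters only if reduction means any fall, or something close to it.

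**What to change.** In the sample size section:

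1. Replace the single 80% with the exact power at 40 evaluable patients under the test to be used (73% for Fisher's test at 30% v 75%). Add a short table over placebo rates from 30% to 60% or 70%, once with heparin held at 75% and once with the odds ratio held at 7.
2. State that 30% v 75% refers to a fall larger than the spontaneous one, and give the basis for both rates or say that they are assumptions.
3. Fix that fall, as a log10 change from Day 0, before unblinding.

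Falls pooled over both arms while still blinded may help to avoid a threshold that almost everyone or almost no one meets. They should not be presented as confirming the 30%: in equal arms, 30% v 75% and 52.5% v 52.5% give the same pooled proportion, (30 + 75)/2 = 52.5%.

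The cost is some wording and one table, with no extra patients or procedures. The downside is that the stated power becomes less favourable.
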